### 10.3.2.3 Primary Assisted Patency/Secondary Patency

The primary assisted patency and secondary patency endpoints are specified below in Table 5.

**Table 5. Primary Assisted Patency and Secondary Patency Endpoints**

Outcome Scenarios	Primary Patency	Primary Assisted Patency	Secondary Patency
Patent (DUS, Venogram) at 12 months, no CD-TLR and no TLR before 12 months	Success	Success	Success
Binary Restenosis/Occluded (DUS, Venogram) at 12 months, and no TLR (not clinically driven) before 12 months	Failure	Failure	Failure
TLR (not clinically driven) before 12 months, before any CD-TLR , before 12 month imaging	Missing	Missing	Missing
Patent Venogram, DUS) at 12 months, CD-TLR before 12 months due to restenosis but no occlusion	Failure	Success	Success
Patent (Venogram, DUS) at 12 months, CD-TLR before 12 months due to occlusion	Failure	Failure	Success
Image missing at 12 months, CD-TLR before 12 months due to restenosis but no occlusion	Failure	Missing	Missing
Image missing at 12 months, CD-TLR before 12 months due to occlusion	Failure	Failure	Missing

### 10.3.2.4 Stent Fracture/Delayed Stent Migration

These endpoints are reported by core laboratory imaging. The proportion rate of these endpoints will be constructed cumulatively on both stent level and subject level.

**Numerator:** subject/stent with any positive findings determined by scheduled visits and unscheduled image from day 0 to the upper limit of the imaging reporting window specified in Table 4.

**Denominator:** all *qualified* subjects/stents at a given visit – all subjects/stents with completed and evaluable imaging as part of the scheduled visit, or with unscheduled imaging within the imaging reporting window specified for that visit (all imaging data should be evaluable), plus subjects/stents with positive findings before that timepoint.

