## 10.13 Deviation Handling

A deviation is any event in which the study is not conducted according to the CIP and/or agreement. Deviations may include, but are not limited to the following:

- Failure to obtain informed consent prior to participation
- Incorrect version of the informed consent form used
- Failure to obtain Ethics Board approval before the start of enrolling subjects in the study
- Included subject did not meet inclusion/exclusion criteria
- Required testing and/or measurements not done or incorrectly done
- Subject did not complete follow-up visit
- Follow-up visit was completed outside window
- Unauthorized use of Abre system(s)
- Adverse events/UADE or device deficiencies not reported in the required timeframe by country regulation or as specified in the CIP
- Control of study devices not maintained
- Source data permanently lost
- Enrollment of subjects during lapse of Ethics Board approval
- Subject inclusion limits exceeded

The investigator is not allowed to deviate from the CIP, except when necessary to protect the life or physical well-being of a subject in an emergency situation. Deviations must be reported to Medtronic on the Deviation eCRF.

In the event the deviation involves a failure to obtain a subject's consent, or is made to protect the life or physical well-being of a subject in an emergency, the deviation must be reported to the Ethics Board as well as Medtronic as soon as possible but no later than five (5) working days from the date of the deviation occurrence.

Reporting of all other deviations should comply with Ethics Board policies, local laws, regulatory agency requirements and must be reported to Medtronic as soon as possible upon the center becoming aware of the deviation.

Refer to **Table 16** and **Table 17** for geography-specific deviation reporting requirements and timeframes for reporting to Medtronic and/or regulatory bodies.

The COVID-19 global pandemic started during the 24-month follow-up phase of this study. If a protocol deviation is related to COVID-19, details must be reported as to how the deviation is related to the pandemic. Examples include: Patient preference – declined / did not feel safe and/or comfortable; Patient in quarantine however not tested positive with COVID-19; Research staff – site staffing issue due to COVID-19; Institutional policy – no research activities permitted on site, etc.

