### 7.9.3 Secondary Endpoints

To assess how the subjects are doing clinically, the following secondary endpoints will be evaluated. All secondary endpoints will be evaluated using descriptive statistics. No inferential analyses are planned. Detailed analysis methods for core laboratory endpoints and endpoints assessed by office visits can be found in Section 10.

In addition, time-to-event analysis will be performed and Kaplan Meier (KM) estimates with two-sided 95% confidence interval using Peto formula will be reported for major adverse events (MAE) and its component events through 12 months, and annually through 36 months.

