**Table 4. Imaging reporting window**

Study Visit	Target Day	Reporting Window
Index Procedure	Day 0	NA
30-Day	Day 30	NA
6-Month	Day 180	NA
12-Month	Day 360	Study Day 271 – 420

Study Visit	Target Day	Reporting Window
24-Month	Day 720	Study Day 421 – 780
36-Month	Day 1080	Study Day 781 – 1140

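### The cumulative stent fracture and delayed migration rates keep every earlier positive in the denominator but drop earlier negatives who are not re-imaged, so the 24- and 36-month rates can overstate incidence

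*SAP*

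**What the plan says.** SAP 10.3.2.4 sets one rule for stent fracture and delayed stent migration: "The proportion rate of these endpoints will be constructed cumulatively on both stent level and subject level".

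- **Numerator:** any positive finding "from day 0 to the upper limit of the imaging reporting window specified in Table 4".
- **Denominator:** "all subjects/stents with completed and evaluable imaging as part of the scheduled visit", or with evaluable unscheduled imaging inside that visit's window, "plus subjects/stents with positive findings before that timepoint".

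The windows in SAP Table 4 do not overlap: "Study Day 421 – 780" for 24 months and "Study Day 781 – 1140" for 36 months. Protocol 10.12.6.4 requires X-rays of all subjects at 12, 24 and 36 months.

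No other planned analysis covers these two endpoints. Kaplan-Meier estimates are planned for primary patency (SAP 7.9.1.2), for MAE and its components (SAP 7.9.3) and for TLR (Protocol 14.4.2). Multiple imputation and the tipping-point analysis (SAP 7.4) concern primary endpoints only.

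**The concern.** Whether a subject stays in the denominator depends on outcome. A subject with a fracture at 12 months counts at 24 and 36 months whether or not imaged again. A subject with clean X-rays at 12 and 24 months and none at 36 is absent from the 36-month rate. The result is neither the prevalence among those imaged nor a cumulative incidence.

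These proportions are the only planned summaries of fracture and delayed migration at 24 and 36 months. Long-term safety is part of the stated purpose of the post-approval phase (Protocol 5.2). A change between visits could be taken for a change in device behaviour when only the completeness of imaging had changed.

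**Working it through.** The documents state no fracture or migration result and no share of missed X-rays, so there is no figure of the plan to reproduce. The rule is applied directly.

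**Inputs**
- 200 subjects implanted and 302 stents used (Protocol 7).
- Fracture rate of 1.4% in the literature review (Protocol Appendix A, Table XII), used only for scale. It is about 3 of 200 subjects or 4 of 302 stents.
- Share of earlier negatives not imaged at the later visit, m: assumed, with a range shown.

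**1. No new events after 12 months.** With E positives among N units, all imaged at 12 months, the rule gives E / [E + (N − E)(1 − m)].

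Subjects, E = 3 and N = 200 (3/200 = 1.50% when none is missed):

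| m | Calculation | Rate | Excess (points) |
|---|---|---|---|
| 20% | 3/(3 + 197 × 0.8) = 3/160.6 | 1.87% | 0.37 |
| 30% | 3/(3 + 197 × 0.7) = 3/140.9 | 2.13% | 0.63 |
| 40% | 3/(3 + 197 × 0.6) = 3/121.2 | 2.48% | 0.98 |

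Stents, E = 4 and N = 302: 4/302 = 1.32% becomes 4/(4 + 298 × 0.8) = 1.65% at m = 20% and 4/(4 + 298 × 0.6) = 2.19% at 40%.

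A life table gives 1 − (1 − 3/200)(1 − 0)(1 − 0) = 1.50% at 24 and 36 months for every m.

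**2. New events, missing at random.** Let p be the risk by 12 months and q the risk in the next interval.
- Rule: [p + (1 − p)(1 − m)q] / D, with D = p + (1 − p)(1 − m).
- True cumulative risk: p + (1 − p)q.
- The event-free share under the rule is the true event-free share times (1 − m)/D. Since D − (1 − m) = pm, that factor is below 1 whenever p > 0 and m > 0, so the rule is then always too high.

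With p = q = 1.4%, the true value is 0.014 + 0.986 × 0.014 = 2.78%.
- m = 20%: (0.014 + 0.986 × 0.8 × 0.014)/(0.014 + 0.986 × 0.8) = 0.02504/0.8028 = 3.12%.
- m = 40%: 0.02228/0.6056 = 3.68%.

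**3. Direction between visits.** Take E = 3, no new events, 30% of negatives missed at 24 months and 10% at 36 months. The rate is 2.13% at 24 months and 3/(3 + 197 × 0.9) = 3/180.3 = 1.66% at 36 months. A cumulative rate has fallen with no change in events.

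**4. Where the inflation disappears.**
- No earlier positive (p = 0): the rule gives q for any m, so there is no bias.
- Informative missingness: keep p = q = 1.4% and m = 20% for negatives. The negatives imaged are 0.986 × 0.986 × 0.8 = 0.7778. If 40% of the new positives are missed, the numerator is 0.014 + 0.0138 × 0.6 = 0.0223 and the rate is 0.0223/(0.0223 + 0.7778) = 2.79%, almost exactly the truth. If more than about 40% are missed, the rule understates.

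**The case against.** **The convention has a reason.** A denominator of events plus adequate follow-up runs through the SAP (10.2, 10.3.1, Table 3). Positives must be retained: a subject whose stent is explanted is followed for only 30 days more (Protocol 10.11), and dropping such subjects would lose device failures. This stands. The fault lies in how negatives are treated. For clinical endpoints a late contact keeps an event-free subject evaluable. Here only an image does, and a phone encounter (Protocol 10.10) supplies none.

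**Unscheduled images count over windows of about a year.** True, but Protocol 10.11 defines unscheduled visits as those with an intervention in the target vein. An event-free subject who misses a visit would seldom have one.

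**The example starts from complete 12-month imaging.** This is fair. The plan itself allows 20% loss on the effectiveness endpoint, and only loss beyond the 12-month level inflates the later rates. Starting from 3/160 = 1.88%, later denominators of about 141 and 121 give 2.13% and 2.48%, an excess of 0.25 and 0.60 points.

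**Counts will be visible.** SAP 7.2 requires numbers with percentages, and subject listings. A reader who sees 3/200 and then 3/141 can work out what happened. This limits the harm but does not make the percentage a cumulative incidence.

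**Stronger readings that the documents do not support.**
- A reader might infer that stent integrity is a main purpose of the extended follow-up. The post-approval primary endpoint is TLR (Protocol 6.3.1), and fracture is one of sixteen secondary endpoints.
- A reader might infer that many X-rays were missed. Protocol 10.13 says only "The COVID-19 global pandemic started during the 24-month follow-up phase of this study" and lists example reasons for deviations. It gives no count, and Protocol 10.10 tells sites to keep seeking an in-clinic visit.
- A reader might infer that the rates must climb and will suggest late device fatigue. They need not: steps 3 and 4 show a fall, no bias and a reversal.

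**Conclusion.** The point holds conditionally. By its wording, the rule in SAP 10.3.2.4 makes retention in the denominator depend on outcome, and no other planned analysis offsets this. The rates overstate cumulative incidence if at least one positive precedes the visit and missed imaging is unrelated to fracture or migration.

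For rare events with no new ones, the relative inflation is about 1/(1 − m). In absolute terms it is modest: 0.4 to 1.0 percentage points for 3 positives of 200 with 20% to 40% of negatives missed, and less if 12-month imaging was already incomplete. The missed share is an assumption throughout.

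SAP 7.9.3 makes these endpoints descriptive. No test, performance goal or success criterion is affected, and under random missingness the error runs against the device. This is a desirable improvement and does not threaten the trial's conclusions.

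**What to change.** In SAP 10.3.2.4, define the cumulative rate for each endpoint by a visit-interval life table or an interval-censored estimate, with negatives censored at their last evaluable image. Kaplan-Meier on image dates is acceptable as an approximation. For stent-level rates, use intervals that allow for several stents in one subject (302 stents in 200 subjects). Beside each estimate, show the number imaged and the number newly positive at that visit.

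The at-visit proportion should not replace the cumulative estimate, because it loses earlier positives who are no longer imaged. A fixed denominator of all implanted subjects is not a repair either: with p = q = 1.4% and 20% missed it gives 0.014 + 0.986 × 0.8 × 0.014 = 2.50% against a true 2.78%.

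The cost is one added descriptive analysis per endpoint, from image dates and core laboratory readings that are already collected. Two limits remain and should be stated with the result: event timing is known only to the visit interval, and the estimate assumes non-informative censoring.

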### 10.3.3 Endpoints Assessed by Clinic Visit

Endpoints assessed by clinic visit include EQ5D VCSS Scores, etc. These assessments/endpoints are obtained/determined through the clinic visit assessment. If the clinic visit (scheduled and unscheduled) is not completed then these assessments will not be available, and therefore will be treated as missing values and will be excluded from the analysis.

For the assessments that are recorded on the scheduled visit forms regardless of window, the scheduled visit data will be used in the analyses.

For subjects that don't have any assessment for a scheduled visit (visit not done or the visit is completed but the assessment is not readable), the following rules will be used to slot the unscheduled visit assessments:

- 1.) Assessments will be slotted into each study visit (including scheduled and unscheduled visit) using the visit date, visit window is described in Table 6.
- 2.) The assessments with unevaluable values will be excluded from the visit slotting step;

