## 10.10 24 and 36 Months ( $\pm$ 30 days) Post-Procedure Follow-Up Assessment

Subjects will be seen in the office at 24 months (690-750 days) and 36 months (1050-1110 days) post-procedure. The following evaluations will be completed and data recorded on the Follow-up eCRF:

- Physical assessment of limbs;
- Villalta Score and VCSS (both limbs);
- Quality of Life Questionnaires: EQ-5D and VEINES-QOL/Sym;
- INR for subjects on warfarin;
- Duplex Ultrasound (target limb);
- Duplex ultrasound (contralateral limb); image of the CFV waveform only.
- X-ray (target limb);
- Adverse events/device deficiency;
- Medications: Antithrombotics, Antibiotics, Immunosuppressants, NSAIDs, Steroids, Diuretics, Calcium-channel blockers, Statins;
- Discontinuation information (in case the subject ends involvement in the study).

In the event that an in-clinic 24 and/or 36 Month visit is unable to be performed (i.e. Missed Visit) a 'Phone Encounter' may be completed. The purpose of the 'Phone Encounter' is to capture subject status including the following:

- Date of contact (phone encounter)
- Medications: Antithrombotics, Antibiotics, Immunosuppressants, NSAIDs, Steroids, Diuretics, Calcium-channel blockers, Statins;
- Adverse events/device deficiency;

The 'Phone Encounter' does not replace the 24- and/or 36-month visit. If a 'Phone Encounter' is completed for the 36-month visit, the subject should not be immediately exited from the study. The site should continue to attempt to schedule an in-clinic visit as specified above when it is appropriate to do so and work with Medtronic to understand how long the study will remain open.

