## 10.11 Unscheduled Visits

Unscheduled visits are additional non-scheduled visits that occur at times other than the predetermined intervals and during which an intervention in the target vein takes place. If the Abre stent(s) is(are) explanted, the subject will be followed for safety reporting only for 30 days post-explant. AE data should be collected on the AE eCRF, and study exit data should be collected on the Study Exit eCRF. It is not allowed to implant a new Abre stent during the reintervention. The following assessments will be completed and the data will be recorded on the Follow-up eCRF:

- Physical assessment of limbs
- Villalta Score and VCSS (for both limbs, should be taken before any intervention)
- Quality of Life Questionnaires: EQ-5D and VEINES-QOL/Sym (should be taken before any intervention)
- INR for subjects on warfarin
- Duplex ultrasound (target limb)
- Duplex ultrasound (contralateral limb); image of the CFV waveform only.
- Venogram (target limb)
- IVUS (target limb)
- Plain X-ray (target limb) is required pre and post re-intervention to assess for stent fracture

- Secondary procedure data
- Adverse events/device deficiency
- Medications: Antithrombotics, Antibiotics, Immunosuppressants, NSAIDs, Steroids, Diuretics, Calcium-channel blockers, Statins
- Discontinuation information (in case the subject ends involvement in the study)

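### Symptom and quality-of-life change is summarised only over subjects with a score at each visit, with no missing-data method, so means at successive visits can come from different subjects

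*SAP*

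**What the plan says.** SAP 7.11 plans to report change from baseline in the four scores at 6, 12, 24 and 36 months, and SAP 7.9.3 makes all secondary endpoints descriptive. SAP 10.3.3 sets the rule for absent scores: "If the clinic visit (scheduled and unscheduled) is not completed then these assessments will not be available", and they are then "treated as missing values and will be excluded from the analysis".

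Two provisions limit the exclusion:
- "For the assessments that are recorded on the scheduled visit forms regardless of window, the scheduled visit data will be used in the analyses".
- Where a scheduled visit has no usable score, "the following rules will be used to slot the unscheduled visit assessments". The windows in SAP Table 6 are days 421-780 for 24 months and days 781-1140 for 36 months.

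Missing-data methods appear elsewhere but do not reach these scores. Multiple imputation (SAP 7.4.1, protocol 14.6) is for the primary effectiveness endpoint. The tipping-point analysis (SAP 7.4.2) is for the two primary endpoints.

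Earlier scores on the same subjects are scheduled. Protocol 10.12.3 has Villalta and VCSS at baseline, 30 days, 6 and 12 months before the late visits. Protocol 10.12.4 has the questionnaires at baseline, 6 and 12 months.

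**The concern.** A mean over available scores estimates the mean for all subjects only if having a score is unrelated to its value. The protocol describes three ways in which late scores can be lost:
- When "an in-clinic 24 and/or 36 Month visit is unable to be performed", a phone contact may be made (protocol 10.10). It records the contact date, medications, adverse events and device deficiencies, but no scores.
- After an explant, "the subject will be followed for safety reporting only for 30 days post-explant" (protocol 10.11).
- "The COVID-19 global pandemic started during the 24-month follow-up phase of this study" (protocol 10.13). SAP version 4.0, dated February 2020, has no provision for this.

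If subjects who are doing worse have fewer late scores, the 24- and 36-month means look better than the cohort is. A benefit that appears to be maintained from 12 to 36 months could then partly reflect who was still measured. The scheduled 6- and 12-month scores carry information about the absent subjects, and the plan does not use it for the later means.

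Protocol 10.14.3 also says that subjects who leave early remain in the analysis of results. SAP 10.3.3 does not say how that is met for these endpoints at visits after they leave.

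**Working it through.** **The plan's own figure.** There is none to reproduce. Neither document gives an SD, a sample size, an expected missing rate or a power for the score endpoints. The only long-term loss figure is 20%, allowed for 12-month patency (SAP 6.3): 160 / (1 - 0.20) = 200.

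**Step 1: identity.** With a proportion d missing,

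bias of the available-case mean = d x (mean of observed - mean of missing).

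If the two groups have the same mean, the bias is zero whatever d is. For the Villalta score, with assumed gaps of 1 to 6 points and d of 10-30%:
- smallest: 0.10 x 1 = 0.1 points
- at 20% missing and a 2-point gap: 0.20 x 2 = 0.4 points
- largest: 0.30 x 6 = 1.8 points

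For scale, protocol Appendix A Table XIV gives a literature change of 17.3 - 6.6 = 10.7 points, without an SD. With an assumed SD of 6 and 160 observed subjects, the standard error is 6 / sqrt(160) = 0.47 points.

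**Step 2: a mechanism for the gap.** Assumptions, none from the documents: 200 subjects, correlation 0.6 between visits, 15-35% missing at 36 months, and log-odds of missing rising by 0.5 to 1.0 per SD of worse score.

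| Absence driven by | Available-case bias (too favourable) | Bias left after using earlier scores |
|---|---|---|
| Earlier score | about 0.04-0.17 SD | essentially none |
| 36-month score itself | about 0.07-0.29 SD | about 0.04-0.17 SD (56-59% of it) |

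The two bias ranges are linked. When absence follows the earlier score, the selection reaches the 36-month score only through the correlation: 0.6 x 0.07 = 0.04 and 0.6 x 0.29 = 0.17. The standard error of the estimate that uses earlier scores was equal or smaller in both cases.

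At 20% missing, with absence following the earlier score, the bias is 0.06-0.10 SD. The standard error is 1 / sqrt(160) = 0.08 SD.

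**Step 3: the same on the Villalta scale.** Assumptions: SD 6, and odds of a missing score doubling per SD of worse 12-month score. The overstatement of improvement, in points, by 12-to-36-month correlation:

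| Missing | 0.3 | 0.5 | 0.7 |
|---|---|---|---|
| 10% | 0.11 | 0.19 | 0.27 |
| 20% | 0.23 | 0.39 | 0.54 |
| 30% | 0.34 | 0.57 | 0.79 |

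Using the 12-month score leaves about 0.01 points or less.

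**Step 4: an effect that can run the other way.** Protocol 10.11 defines unscheduled visits as those "at times other than the predetermined intervals and during which an intervention in the target vein takes place", with scores taken before the intervention. Under Table 6, a pre-intervention score from as early as day 421 can stand as the 24-month value. Such subjects are likely to be symptomatic, so slotting them can pull the mean towards less benefit. Steps 2 and 3 do not model this.

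**The case against.** The endpoints are secondary and descriptive, the post-approval phase has no hypothesis test (protocol 14.5), and available-case summaries are a normal way to describe what was observed. That stands. It is why the model belongs beside the planned summaries and should not replace them.

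A reader might infer that every subject who misses a visit is dropped. The documents do not support this, because out-of-window scheduled visits count and unscheduled ones can be slotted. Protocol 10.10 also says that a phone contact does not replace the visit. At 36 months, sites should not exit the subject immediately and should keep trying for a clinic visit.

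A reader might also infer that the protocol makes score-related absence likely. It does not show this. Several of the pandemic reasons it lists (institutional policy, site staffing, quarantine) are plausibly unrelated to venous symptoms. Nothing is said about who needs a phone contact, and no explant frequency is given.

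Finally, the near-complete correction in Step 2 follows from the assumption that absence depends on an observed score. If it depends on current status, more than half of the bias remains. That also stands, but a partial correction with no loss of precision is still better than none.

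**Conclusion.** The point holds as a minor improvement. The available-case rule is explicit, no missing-data method covers the four scores, and scheduled earlier scores that could inform the late means are not used for that purpose. Means at different visits can therefore describe different subjects.

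The stronger conclusion, that the plan overstates long-term benefit, is not supported. The documents give no missing rate or mechanism, so size and direction are unknown. The bias is zero if absence is unrelated to the scores, and slotted pre-intervention scores could reverse it. The ranges of 0.04-0.17 SD and 0.07-0.29 SD rest wholly on the assumptions in Step 2. No performance goal, test or success criterion is affected. What is at stake is how the reported 24- and 36-month symptom and quality-of-life means are read.

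**What to change.** Keep the available-case summaries. SAP 7.2 already requires the sample size with each. Add to SAP 10.3.3 and 7.11, as supportive analyses:

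1. One likelihood-based repeated-measures model per score, using all observed scores, with visit, baseline score and venous disease category as terms and an unstructured covariance. Report the estimated mean change at 6, 12, 24 and 36 months.
2. A stated rule for scores after death or explant. Without one, the model implicitly extrapolates scores for subjects who have died, and treats explanted subjects as if still stented, which changes the quantity estimated.
3. A comparison of baseline and 12-month scores between subjects with and without a 24-month value, and likewise for 36 months.

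The cost is a little extra analysis work, with no new data or visits. The model corrects fully only if missingness depends on observed scores. Otherwise the correction is partial: about 40% of the bias was removed in the less favourable setting of Step 2.
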